5.5 Use of radiation: N/A

5.6 Use of Center for Magnetic Resonance Research: All MRI scanning will occur on a 3-Tesla MRI scanner managed by the CMRR.

6.0 Data and Specimen Banking

6.1 Storage and Access: Saliva samples will be stored in a -20 degree freezer and hair samples will be stored in a dry dark secure location until they can be batched with other samples for hormonal assay. Any material

remaining after the planned assays will be discarded. No tissue or biological samples will be stored for future use or shared.

Biospecimen samples will be identified only with a unique study ID, child sex, and sample number. No PHI will be associated with any biospecimen samples. Samples will not identify the study condition of interest (i.e., social buffering condition).

6.2 Sharing: De-identified data will be shared with qualified researchers when requested for scientific purposes including replication of results, use in meta-analyses, or appropriate extension of analyses. No biospecimen samples will be saved or shared.

7.0 Sharing of Results with Participants

7.1 Results will only be shared with participants in aggregate, with the following exceptions:

Regarding hormonal or physiological measures in this study, abnormal values are commonly due to an interfering substance present in the sample (e.g., milk for salivary cortisol) or motion artifact in the case of EKG.

Without a body of evidence, it seems unethical to alarm families given an out-of-range assay value and therefore we do not plan to share individual results with participant.

In the event that the scanner operator or study personnel see something unusual in the MRI scan, the images will be submitted for review by a radiologist. Images contain only the study ID number, participant's age in years, participant sex, and test date. In the event that the radiologist determines that the incidental finding should receive clinical follow-up, we will share this information with the parent(s) of the minor child participant with the recommendation to consult with the child's primary care physician. Incidental findings from research scans are not clinically diagnostic and the images may not be added to the child's medical record.

8.0 Study Population

8.1 Inclusion Criteria: Healthy 10- to 15-year-olds. Additional inclusion criteria ensure that youth will be able to follow the study procedures (have sufficient vision, hearing, and language skills to provide verbal and written assent, see and read stimuli presented on the computer screen, and hear verbal instructions provided by the experimenter and/or judges).

8.2 Exclusion Criteria for child participation: Premature birth (less than 37 weeks), congenital and/or chromosomal disorders (e.g. cerebral palsy, FAS, mental retardation, Turner Syndrome, Down Syndrome, Fragile X), Autism Spectrum Disorders, history of serious medical illness (e.g., cancer, organ

transplant), youth using systemic glucocorticoids or beta-adrenergic medications, diagnosed psychiatric illness or psychotropic medication, seizure disorder or other neurological disorder, academic delay or individualized education plan (IEP), contraindications for MRI (implanted medical device; presence of non-removal metal in or on the body, including piercings, orthodontic braces or certain permanent retainers), known pregnancy, tattoo, or history of significant claustrophobia.

8.3 Screening: Screening will occur by asking parents questions at the time of telephone recruitment. To reduce confounding of age and pubertal stage, we will use a stratified recruitment method. During recruitment, parents will be asked 3 questions about their child's physical development, and children will be initially categorized into Pre/Early and Mid/Late Puberty. As cells fill, participants will no longer be enrolled into those cells. Also, to increase minority representation we will sample across zip codes with higher racial and ethnic minority representation.

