The **long-term goal** of our research is to enrich understanding of threat-related stress regulation and its role in human development. The **overall objective** of this project is to understand normative processes in threat-related stress regulation and their neurobiological correlates as children leave childhood and become more autonomous in adolescence. The **central hypothesis** of this project is that early adolescence is a period of time when parental buffering wanes in efficacy, leaving many youth experiencing a relative dearth of relationships that can provide powerful stress buffers.

The aim of the current study is to delineate changes in brain activation in response to social buffering by parents and friends over the pubertal transition.

Hypothesis #1: Parental social buffering will result in increased activation in brain regions associated with safety (e.g. vmPFC) and lower activation in brain regions involved in fear and pain (e.g., insula, amygdala, hypothalamus), as well as tighter coupling between the vmPFC and amygdala activity, but these relationships will wane with pubertal development.

Hypothesis #2: Friend social buffering will result in less attenuation in the same brain regions, and less mPFC-Amygdala coupling than parental buffering, but will also become less effective with pubertal development.

Hypothesis #3: Neural activity associated with social buffering will mediate the effectiveness of physiological buffering by social partners.

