4.2 Drug/Device Handling: N/A

4.3 Biosafety: N/A

4.4 Stem Cells: N/A

5.0 Procedures Involved

5.1 Study Design: The study design is cross-sectional. 150 target children (10- to 15-year-olds) will be randomly assigned to one of three conditions: (1) no social support (standard MRI scanning condition); (2) presence of a parent; or (3) presence of a close friend. Outcome measures will be compared across the three social buffering conditions. Pubertal stage will be included as a continuous variable in analyses of physiological and/or brain responses.

Two tasks will be used during the MRI scanning. Both have been shown to activate stress-related regions of the brain in past studies and have been used by our labs. The order of these two tasks will be counterbalanced.

Based on the results of piloting social buffering will EITHER be done with the presence of a buffer in person, or, displayed on screen via a live Zoom feed. All conditions will use the same modality.

Study Overview:

Visit 1: Parent and child will participate in an online video session (via Zoom) lasting approximately 2 hours. Following a detailed overview of study and consent/assent procedures, participants will be asked to complete the following measures:

Parent:

- Questionnaire regarding family income, education level, and family composition
- Parent-report questionnaire about child's general health, behavior, and development (MacArthur Health Behavior Questionnaire; HBQ)
- Parent-report MRI safety screening questionnaire about the child to rule out any contraindications for MRI scanning
- *[If the child is randomized to the parent-present buffering condition],* self-report MRI safety screening questionnaire to rule out any contraindications for sitting in the MRI area

PROTOCOL TITLE: An MRI Study of Learning and Social Support

VERSION DATE: v.10 2024.12.18

- Child life challenges question

Children/adolescents:

- Questionnaire about general health, behavior, and development (MacArthur Health Behavior Questionnaire; HBQ)
- Questionnaire about their relationships with their parents and their best friend (Network of Relationships Questionnaire)
- Questionnaire about anxiety in different contexts (State-Trait Anxiety Inventory for Children)
- Pubertal development questionnaire (Morris and Udry, 1980)
- Safety screening questionnaire to confirm safety in the MRI scanner
- Perceived stress questionnaire
- Child life challenges questionnaire

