The primary analyses will consist of a series of multiple regression models. For each dependent variable, variation in neural activity, cortisol, and physiological responses, we will begin by testing the three-way interaction between social buffering condition, sex, and pubertal stage for all outcomes. If the three-way interaction is not significant, we will then examine all two-way interactions. If the two-way interactions are not significant, we will then examine main effects only models. If the three-way interaction is significant, we will not examine any other model. If condition is significant as an interaction or as a main effect, we will examine all pairwise comparisons using Tukey's Honestly Significant Difference test.

Multiplicity of testing. We will correct for multiple comparisons using the Benjamini-Hochberg (BH) correction. The BH method works by controlling the false discovery rate, and relative to the Bonferroni's correction is more powerful, while still adequately protecting against Type I error (Williams, Jones, & Tukey, 1999).

Mediational Analysis. When changes in activity of brain regions differ by condition or condition by pubertal status and we also see condition or condition by pubertal status differences for cortisol or physiological measures, then we will examine whether brain activity differences mediate the neuroendocrine or physiological differences. This will be examined using path analysis, while controlling for covariates identified in the preliminary covariate analysis, and will be estimated using the lavaan package in R (Rosseel, 2012).

The significance of all indirect effects will be assessed using bias-corrected 95% confidence intervals (Efron & Tibshirani, 1986), where confidence intervals that are non-overlapping with zero will be considered significant.

Power Analysis for the Mediational Analysis: To assess power to detect mediation, we performed a Monte Carlo-based power analysis using simulated data. We varied the parameter values to roughly correspond to Cohen's criteria for small, medium, and large effects. This resulted in a total of 27 conditions, which we examined at our target sample size of 200. Each

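### The puberty-only recruitment cells described in section 8.3 do not separate age from puberty, and no condition × age term is planned, so waning of buffering with age can be reported as waning with puberty

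*Combined protocol and SAP*

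**What the plan says.** **Recruitment.** Section 8.1 admits "Healthy 10- to 15-year-olds". Section 8.3 gives the aim of the stratification ("To reduce confounding of age and pubertal stage, we will use a stratified recruitment method") and then the mechanism: "children will be initially categorized into Pre/Early and Mid/Late Puberty. As cells fill, participants will no longer be enrolled into those cells". No age band or age-within-puberty quota is described anywhere.

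**Model.** Section 5.1 states: "Pubertal stage will be included as a continuous variable in analyses of physiological and/or brain responses". For the primary analyses, section 15.3 says "we will begin by testing the three-way interaction between social buffering condition, sex, and pubertal stage for all outcomes", then steps down to two-way interactions and main effects. Age is not named among these terms. It could enter only through the covariate screen in section 15.1, as a control variable; no covariate-by-condition term is described.

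**Claim.** Hypothesis 1 in section 2.3 expects parental buffering to act on the brain regions of interest and adds that "these relationships will wane with pubertal development". Hypothesis 2 makes a similar claim for friends. Under section 15.3, a condition-by-pubertal-status difference in both brain and physiological measures opens the mediation analysis.

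**Data.** Section 5.2 has birthdate collected, so exact age is available.

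**The concern.** Between 10 and 15 years, age and pubertal stage rise together. Filling a Pre/Early and a Mid/Late cell fixes how many children fall in each, but does nothing to make older early-puberty or younger late-puberty children more common. The mechanism as described does not deliver its stated purpose.

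The model does not make up for this. If buffering weakens because children get older, for social or cognitive reasons unrelated to puberty, the condition × puberty term picks up part of that effect.

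The rival explanation is a live one in the protocol itself. Section 2.2 reports full parental buffering at 9–10 years and none at 15–16, which is a pattern by age, alongside a pubertal pattern at 11–14. At stake is the interpretation of Hypotheses 1 and 2. Hypothesis 3 is also affected where a condition-by-puberty finding triggers mediation.

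**Working it through.** **1. The plan's own figure.** Section 15.2 gives a minimum detectable f² for the three-way term of 0.056 at n = 200 and 0.070 at n = 160 (alpha .05, power .80, 12 covariates). With three conditions the test has u = 2. The model has 12 + 4 main + 5 two-way + 2 three-way = 23 terms, so v = 200 − 24 = 176 and 160 − 24 = 136. The noncentral F with λ = f²(u + v + 1) gives 0.0548 and 0.0709. Power at the stated values is 80.9% and 79.5%. The figures reproduce within 2 points of power. This model contains no condition × age term.

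**2. What puberty-only cells do.** Assumptions: ages uniform from 10 up to the 16th birthday, puberty linearly related to age, cells split at the median and filled equally.
- Population correlation .70: puberty-only cells leave .70. Crossing puberty with two age bands (10–12, 13–15) gives about .46–.47.
- A second simulation with five discrete stages and a 0.5-stage sex difference: no quota against puberty quota gave .80/.81, .70/.71 and .55/.55. With earlier puberty it gave .79/.82, .69/.73 and .54/.57. The Mid/Late cell stayed 1.7–2.5 years older on average.

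**3. Why an age main effect does not help.** Let age and puberty be standardised with correlation r, with three equal groups, and let age alone moderate the parent effect with slope β.
- Without age in the model, the parent-versus-control puberty slope converges to rβ.
- With a common age slope γ, least squares gives γ = β/3. The puberty slope is then r(β − β/3) = 2rβ/3 in the parent group and −rβ/3 in the others. The difference is again rβ.
- At β = 0.5 the spurious slope is 0.25 (r = .5), 0.325 (.65) or 0.40 (.8).

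**4. How often this is significant.** Simulated two-way F test, n = 150 (the analysed sample in section 10.1), alpha .05. The low end of each false-positive range is β = 0.3 and the high end β = 0.5; ranges also cover repeated simulations. The last column is power for a true puberty slope of 0.5 SD per SD with no age moderation.

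| r | False positive, age as main effect | False positive, condition × age added | Variance factor 1/(1 − r²) | Power: planned → adjusted |
|---|---|---|---|---|
| .5 | 10–22% | about 5% | 1/0.75 = 1.3 | about 70% → 54–58% |
| .65 | 14–34% | about 5% | 1/0.5775 = 1.7 | about 70% → 43–50% |
| .8 | 20–51% | about 5% | 1/0.36 = 2.8 | about 70% → 30–31% |

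Omitting age altogether gives nearly the same false-positive rates as the main effect. With no waning at all the rate is 5.1%. The five-stage simulation gave 24–53% at β = 0.5 and 18% at β = 0.3.

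**5. What each remedy does (five-stage simulation, slope 0.5, n = 150).** Crossed cells alone lower the correlation from .55–.82 to .29–.56 but leave 8–23% false findings. Condition × age alone restores about 4–6%, but power for a true puberty slope is 25–51% with puberty-only cells, against 45–63% with crossed cells. The degrees-of-freedom cost is small: the three-way minimum detectable f² at n = 150 moves from 0.0765 to 0.0777 (two extra terms) or 0.0784 (three).

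**The case against.** **The cells may already include age.** A reader might infer that recruitment is definitely stratified on puberty alone. The text does not establish that. The stated purpose makes most sense if age also defines cells, section 8.3 calls the puberty grouping initial, and section 23.1 mentions a cell count without describing it. Equation 1, cited in section 15.2, is not visible in the available text. This stands as a limit on certainty. As written, though, only puberty defines the cells and the verbal description of the model has no age interaction.

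**Age-driven waning would be reported as puberty.** This is also too strong. In most simulated settings the false result appears in a minority of trials, so it can be reported, not will be. Nor does it follow that the two explanations are inseparable: exact age is collected, and what is missing is a pre-specified analysis that uses it.

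**The rates are not those of the full procedure.** Section 15.3 tests the three-way term first and applies Benjamini-Hochberg, whose family is not defined. At an illustrative threshold of .005, the false rates fall to 2–5% (r = .5), 3–10% (.65) and 5–20% (.8). This stands for the size. It does not remove the bias: multiplicity control addresses chance findings, not confounding.

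**The adjusted model could hide a true puberty effect.** This stands. Puberty comes from questionnaires because the nurse exam was dropped (section 5.2), while age is exact. If puberty reliability were .7 (an assumption), adjusted power would be about 40%, 29% and 15% at r = .5, .65 and .8. Making the adjusted model a condition for any claim would be a debatable trade-off.

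**Recruitment may be far advanced.** This is version 10 (December 2024), and section 20.1 shows that some participants had finished by January 2024. How many remain is not stated.

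**Conclusion.** The concern holds in a limited form. The recruitment mechanism as described leaves the age–puberty correlation essentially unchanged, and the models as described contain nothing that separates condition × puberty from condition × age. A condition × puberty result can therefore reflect waning with age.

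For a single two-way test at n = 150, the false-positive rate is about 10–50% under r = .5–.8 and age-only moderation of 0.3–0.5 SD per SD, against about 5% with condition × age fitted. The correlations, slopes and age distribution are assumptions. The direction does not depend on their exact values; the size does, and it would be smaller after Benjamini-Hochberg.

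The documents do not show that age bands are absent in practice, nor that a puberty finding will be wrong. The analysis change is a cheap improvement that affects what the trial can conclude.

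**What to change.** 1. **Analysis.** Beside each planned model that tests condition × puberty, including any that triggers the mediation analysis, pre-specify a model that adds age and condition × age. Report both, with the sample age–puberty correlation. Attribute waning to puberty rather than age only to the extent that the adjusted estimate supports it. Keep this as a side-by-side analysis, not a gate. Cost: plan wording and one extra model per outcome; no new data. The downside to state is the loss of precision in the last column of the table, which is worse if puberty is measured with error.

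2. **Recruitment.** For children still to be enrolled, define the cells as age band × Pre/Early or Mid/Late puberty, or write the age bands into section 8.3 if they already exist. The rarest cell is about 8–14% of children when the puberty cut is near the median (r = .6–.8), and 3–7% with off-centre cuts. Section 23.1 lists 14,529 + 15,284 = 29,813 registry children, so even 3% is about 894 before eligibility and consent. This helps only the remaining enrolment; the fall in correlation from .70 to about .47 assumes quotas applied to the whole sample.

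Both parts are useful. Crossed cells alone still leave false findings, and the extra term alone leaves low power when the correlation is high.

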9.0 Vulnerable Populations

9.1 Vulnerable Populations:

Population / Group	Identify whether any of the following populations will be targeted, included (not necessarily targeted) or excluded from participation in the study.
Children	Targeted Population
Pregnant women/fetuses/neonates	Excluded from Participation
Prisoners	Excluded from Participation
Adults lacking capacity to consent and/or adults with diminished capacity to consent, including, but not limited to, those with acute medical conditions, psychiatric disorders, neurologic disorders, developmental disorders, and behavioral disorders	Excluded from Participation
Non-English speakers	Excluded from Participation
Those unable to read (illiterate)	Excluded from Participation

Employees of the researcher	Excluded from Participation
Students of the researcher	Excluded from Participation
Undervalued or disenfranchised social group	Included/Allowed to Participate
Active members of the military (service members), DoD personnel (including civilian employees)	Included/Allowed to Participate
Individual or group that is approached for participation in research during a stressful situation such as emergency room setting, childbirth (labor), etc.	Excluded from Participation
Individual or group that is disadvantaged in the distribution of social goods and services such as income, housing, or healthcare.	Included/Allowed to Participate
Individual or group with a serious health condition for which there are no satisfactory standard treatments.	Excluded from Participation
Individual or group with a fear of negative consequences for not participating in the research (e.g. institutionalization, deportation, disclosure of stigmatizing behavior).	Included/Allowed to Participate
Any other circumstance/dynamic that could increase vulnerability to coercion or exploitation that might influence consent to research or decision to continue in research.	Excluded from Participation

9.2 Additional Safeguards:

Children are the targeted population for this study. Others that have been checked as “allowed” above are not being intentionally included or excluded. For example, we will not inquire about someone’s membership in a disenfranchised group, nor whether a target child’s parent is on active duty in the military. Our careful consent/assent procedures, designed to

handle research with children, should be sufficient to cover other vulnerable participants who may inadvertently enter our study.

All of the subjects will be children, ranging 10-15 years old. This study focuses on adolescents because our goal is an analysis of the impact of social buffering and puberty on aversive learning systems. Children have been the focus of our research for the past 30+ years. Our staff members are highly trained in working with children and families. The graduate students working on the project will be Child Psychology and/or Child Clinical Psychology Ph.D. students. The undergraduate research assistants will, for the most part, be majoring in child development.

Much of the work will be performed at either the Institute of Child Development or the Center for Magnetic Resonance Research, centers specifically designed to be child-friendly. In addition to testing rooms, each site includes a playroom/waiting room. While many of our participants will be “too old” for the playroom, they will likely find this a very welcoming environment.

Our laboratory has been scanning both typically developing children and adolescents (ages 4-17) and those at risk due to early health or environmental risks for over two decades. We have conducted NIH funded research with child participants at the CMRR for the past 16 years. We are very experienced in putting children at ease in the MRI scanner and ensuring that children are aware that they can stop at any time. We have completed a prior MRI study with 11- to 14-year-olds using a social stress paradigm; therefore, we are confident that we are well positioned to properly inform children about the procedures and to ensure that we are not stressing children beyond normal everyday levels.

Parents provide consent, youth provide assent, and see below where that process is fully described to ensure that youth have full understanding and are free to decline participation.

Individuals or groups with a fear of negative consequences for not participating in research are included/allowed to participate in this research study. These individuals are neither screened for nor excluded, but will be protected through our careful consent/assent procedures. During these procedures, as well as throughout the study sessions, participants are reminded that they are allowed to stop their participation at any time with no consequence. Our staff members are trained and experienced at noticing participants’ apprehension so that they may further discuss an individual’s participation in the study or stop the study procedures all together if necessary.

